**Table 1-1 Schedule of Assessments**

Assessments	Screening	Double-Blind Treatment Period					32-Week Open-Label Continuation Period						Unscheduled or Early Termination b Visit (±3 days)	30-Day Follow-Up c (±3 days)
		Week 1	Week 4	Week 8	Week 12	Week 16 a	Week 20	Week 24	Week 30	Week 36	Week 42	Week 48		
Visit	1	2	3	4	5	6	7	8	9	10	11	12		
Day	-28 to -1	1 (Baseline)	28 (±3 days)	56 (±3 days)	84 (±3 days)	112 (±3 days)	140 (±3 days)	168 (±3 days)	210 (±3 days)	252 (±3 days)	294 (±3 days)	336 (±3 days)		
Informed consent	X													
Demographics and Medical history	X													
Physical examination d	X	X				X		X		X		X	X	X
Vital signs e	X	X	X	X	X	X	X	X	X	X	X	X	X	X
Hematology and serum chemistry f	X g	X	X	X	X	X	X	X	X	X	X	X	X	X
Lipid panel h	X g	X				X	X	X		X		X	X	X
PT, PTT, INR	X g	X				X	X	X		X		X	X	X
TSH	X g	X				X	X	X		X		X	X	X
Urinalysis	X g	X	X	X	X	X	X	X	X	X	X	X	X	X
Supine 12-Lead ECG i	X	X				X						X	X	
Pregnancy test j	X	X	X	X	X	X	X	X	X	X	X	X	X	X
Randomization k		X												
Photographs (optional) l		X				X						X	X	X
Punch Biopsy (optional) m		X				X								
PD whole blood sample n		X		X		X						X	X	X

Assessments	Screening	Double-Blind Treatment Period					32-Week Open-Label Continuation Period						Unscheduled or Early Termination b Visit (±3 days)	30-Day Follow-Up c (±3 days)
		Week 1	Week 4	Week 8	Week 12	Week 16 a	Week 20	Week 24	Week 30	Week 36	Week 42	Week 48		
Visit	1	2	3	4	5	6	7	8	9	10	11	12		
Day	-28 to -1	1 (Baseline)	28 (±3 days)	56 (±3 days)	84 (±3 days)	112 (±3 days)	140 (±3 days)	168 (±3 days)	210 (±3 days)	252 (±3 days)	294 (±3 days)	336 (±3 days)		
PASI Scoring	X e	X	X	X	X	X		X		X		X	X	
PGA Scoring		X	X	X	X	X		X		X		X	X	
DLQI	X	X	X	X	X	X		X		X		X	X	
Study drug administration p		X		X		X						X		
Dispense/Collect study drug Diary q		X				X						X	X	
Concomitant medications		To be collected from the date that the informed consent form is signed until 30 days after last dose of study drug.												
Adverse events														

DLQI = Dermatology Life Quality Index; ECG = electrocardiogram; INR = international normalized ratio; PASI = Psoriasis Area and Severity Index; PD = pharmacodynamics; PGA = Physicians Global Assessment; PT = prothrombin time; PTT = partial thromboplastin time; TSH = thyroid-stimulating hormone.

- a. After Week 16 assessments in the double-blind treatment period, subjects will be given the option to receive KD025 400 mg QD for an additional 32-weeks in an open-label treatment period (end of week 16 assessments through week 48).
- b. Unscheduled visits and the assessments performed are at the investigator's discretion, but may include any or all of those listed. An Early-Termination visit will be scheduled for all subjects who discontinue prematurely from study drug during the double-blind or open-label treatment periods and procedures are to be conducted immediately upon discontinuation.
- c. For all subjects, including those who discontinue from the study prematurely, a Follow-Up visit should occur 30 days (± 3 days) after their last dose of study drug.
- d. Physical examinations will include weight. Height is to be collected only at the Screening visit.
- e. Vital sign measurements will include sitting blood pressure (BP), heart rate, respiratory rate, and temperature after 5 minutes of rest. Refer to Section 7.2.4 for appropriate BP measuring technique.
- f. Refer to Section 7.2.5 for a complete list of required hematology and serum chemistry assessments. If increases in liver enzymes are observed at any time in a subject, refer to Section 9.4.
- g. If laboratory assessments are done within 14 days of Day 1, they do not need to be repeated on Day 1.

- 
- h. Lipid panel to include total cholesterol, triglycerides, high density lipoprotein (HDL) cholesterol, and low density lipoprotein (LDL) cholesterol.
  - i. ECGs are to be performed immediately prior to blood sample collection (tolerance window: -240 minutes to 0 hour) and to be obtained in triplicate after 5 minutes of resting in the supine position (see Section 7.2.5 for additional information).
  - j. Pregnancy tests will be done using urine samples in women of childbearing potential. Subject must have a negative urine pregnancy test documented within the 24-hour period prior to the first dose of study drug. Confirm with serum testing if urine sample is positive.
  - k. On Day 1 (Week 1), prior to dosing, subjects will be randomized to receive 200 mg KD025 once daily (QD), 200 mg KD025 twice daily (BID), 400 mg KD025 QD, 600 mg/day KD025, or matching placebo. On Day 112 (Week 16) after all assessments are complete in the double-blind treatment period, subjects will be given the option to continue in the 32-week open-label treatment period, during which all participating subjects will receive KD025 400 mg QD for 32 weeks.
  - l. Photos will be taken of affected area(s) if the subject agrees to them. Detailed instructions will be provided.
  - m. Punch biopsies from clear unaffected skin and a selected lesion will be collected predose on Day 1 (Week 1) and from the selected lesion on Day 112 (Week 16). Subjects have the option to decline the punch biopsy.
  - n. PD blood samples to be collected predose and 6 hours postdose on Day 1 of Weeks 1 and 8. PD blood samples to be collected predose on Day 1 of Week 16; predose on Day 1 of Week 48 (for those subjects receiving KD025 during the 32-week continuation period), and at the 30-Day Follow-Up visit.
  - o. To be eligible for the study, subjects must have a PASI of  $\geq 12$  at screening and prior to the first dose of study drug, confirmed at Day 1 (Week 1).
  - p. Subjects will take the first dose of study drug in the clinic and at each visit when PD blood samples are collected. Then study drug will be dispensed for home administration. Study drug is to be taken with a meal or within 5 minutes of finishing a meal.
  - q. Subjects will be required to keep study drug diaries in which they will record the date of study drug administrations. These diaries will be dispensed at the Day 1 (Week 1) visit. Final collection will be at Week 16 for those who do not wish to continue into the open-label period. For subjects that continue to the open-label treatment period, a new diary will be distributed at the Week 16 visit and will be collected at the Week 48 visit. For subjects who discontinue the study prematurely, the diary will be collected at the Early-Termination visit.

---

### 3 LIST OF ABBREVIATIONS

AE	adverse event
ACR20	American College of Rheumatology 20%
ALT	alanine aminotransferase
ANC	absolute neutrophil count
ANCOVA	analysis of covariance
AST	aspartate aminotransferase
ATC	anatomical therapeutic chemical
AUC	area under the curve
BA/BE	bioavailability/bioequivalence
BID	twice daily
BP	blood pressure
CFR	Code of Federal Regulations
C max	maximum plasma concentration
DLQI	Dermatology Life Quality Index
DBP	diastolic blood pressure
ECG	electrocardiogram
eCRF	electronic case report form
EMA	European Medicines Agency
FDA	Food and Drug Administration
GCP	Good Clinical Practice
GI	gastrointestinal
GGT	gamma-glutamyl transpeptidase
HDL	high density lipoprotein
IB	Investigator's Brochure
ICF	informed consent form
ICH	International Conference on Harmonisation
IGA	Investigator's Global Assessment
IND	Investigation New Drug
INR	international normalized ratio
IRB/IEC	institutional review board/independent ethics committee
IRT	Interactive Response Technology
Jak	Janus kinase
LDL	low density lipoprotein
LFT	liver functions test
MAD	multiple ascending dose

MedDRA	Medical Dictionary for Regulatory Activities
mITT	modified intent-to-treat
PASI	Psoriasis Area and Severity Index
PD	pharmacodynamics
PE	physical examinations
PGA	Physician's Global Assessment
PK	pharmacokinetics
PT	prothrombin time
PTT	partial thromboplastin time
QD	once daily
QTc(F)	QT interval corrected using Fridericia's formula
ROCK	Rho-associated, coiled-coil-containing protein kinase
SAD	single-ascending dose
SAE	serious adverse event
SAP	Statistical Analysis Plan
SOC	System Organ Class
sPGA	static Physician Global Assessment
SD	standard deviation
SUSAR	suspected unexpected serious adverse reaction
SBP	systolic blood pressure
TEAE	treatment-emergent adverse event
Th17	T-helper 17 cell
TID	three times daily
TNF $\alpha$	tumor necrosis factor alpha
TSH	thyroid-stimulating hormone
ULN	upper limit of normal
US	United States
WHO	World Health Organization
WNL	within normal limits

#### 4 BACKGROUND AND RATIONALE

Psoriasis is an autoimmune disease that affects many parts of the body but is primarily manifested in the skin. It affects 2% to 3% of the population of the world, making it a very common inflammatory autoimmune disease. The most common form of psoriasis, called psoriasis vulgaris, accounts for over 80% of the people with psoriasis. This type of psoriasis appears as raised plaques of dry scaly skin that may affect multiple regions of the body. Psoriasis is graded as mild, moderate, or severe based on the percentage of the body affected and the intensity of the inflammation. Several genetic loci have been associated with psoriasis and the major genetic determinant, psoriasis susceptibility, accounts for up to 50% of the hereditary aspects of the disease. This locus encodes several immune functions as well as epidermis-associated proteins that are expressed and up-regulated in psoriasis. The genetic basis of sensitivity to psoriasis is supported by the fact that there is 70% concordance in identical twins. The pathogenesis of psoriasis is not fully understood. However, it has been recognized that the recently discovered T helper 17 (Th17) cells, which represent highly proinflammatory cells that function in the induction of multiple autoimmune diseases as well as enhancing the clearance of extracellular pathogens, play a critical role in the pathogenesis of psoriasis. Th17 cells secrete IL-17A, IL-17F, and IL-22, which can activate keratinocytes and endothelial cells in the skin. Antibodies directed against IL-17 have been approved by United States (US) Regulatory Authorities. Secukinumab is a human IL-17A antagonist indicated for the treatment of moderate to severe chronic plaque psoriasis in adult patients who are candidates for systemic therapy or phototherapy. It is administered subcutaneously and has demonstrated robust efficacy in 4 well-controlled clinical studies. The primary endpoints for these 4 studies were the proportion of subjects who achieved a reduction in Psoriasis Area and Severity Index (PASI) score of at least 75% (PASI 75) from baseline to Week 12 and treatment success (clear or almost clear) on the Physicians Global Assessment (PGA; modified 2011). An increase of infections was reported, as well as a few exacerbations of Crohn's disease and hypersensitivity.

Another subcutaneous agent, ustekinumab, has been approved for the same indication. Ustekinumab is a human IL-12 and IL-23 antagonist indicated for the treatment of adult patients

(18 years or older) with moderate to severe chronic plaque psoriasis who are candidates for phototherapy or systemic therapy. An increase of infections and a few cases of skin cancer were reported in 2 large placebo-controlled studies.

One oral agent, apremilast (an inhibitor of phosphodiesterase 4), has been approved for the treatment of adult patients with moderate to severe chronic plaque psoriasis who are candidates for phototherapy or systemic therapy. However, safety concerns such as depression, weight decrease, and issues with drug interactions due to a strong cytochrome P450 enzyme induction have been reported. Also, administration requires a titration at initiation due to gastrointestinal (GI) side effects. The efficacy at 16 weeks was relatively less than that observed secukinumab and ustekinumab. In 2 large controlled studies, efficacy results were PASI 75 of 33.1% and 28.8% versus placebo 5.3% and 5.8%, with the static Physician Global Assessment (sPGA) of “clear” or “almost clear” of 21.7% and 20.4% versus placebo 3.9% and 4.4%, respectively. Apremilast is also approved for psoriatic arthritis.

Several Janus kinase (Jak) inhibitors have been studied for the therapy of psoriasis as well as other autoimmune diseases. However, none has been approved for the treatment of psoriasis to date. Tofacitinib is an inhibitor of Jak 3 with somewhat less activity against Jak 1 and Jak 2. It has been approved by the Food and Drug Administration (FDA) as a twice daily (BID) oral medication for the therapy of rheumatoid arthritis and is marketed as XELJANZ®, and has multiple severe infectious and immunologic side effects associated with therapy. Monotherapy with tofacitinib was associated with a modest increase in American College of Rheumatology 20% (ACR20) improvement criteria compared with placebo (57% versus 26%). Ruxolitinib is a Jak 1 and Jak 2 inhibitor that has been approved for myelofibrosis. It has also been associated with severe side effects including bone marrow suppression. Both of the above Jak inhibitors have undergone initial clinical testing in psoriasis, but the side effect profile of this class of inhibitors has been troublesome.

Several studies have been performed with etanercept and adalimumab, both of which block tumor necrosis factor alpha (TNF $\alpha$ ) and have demonstrated efficacy in the therapy of rheumatoid arthritis, but no therapy has been as effective as IL-17 blockade in the therapy of psoriasis.

A number of biologic products have been approved for the treatment of moderate to severe chronic plaque psoriasis. Interestingly, secukinumab, an IL-17 targeting agent, has shown robust efficacy with rapid onset. However, there are still safety concerns and most of these products are parenterally administered. Apremilast, which does not target IL-17, is an approved oral agent with an acceptable risk benefit. An oral agent such as KD025, which targets IL-17, could potentially provide an oral treatment option with an improved safety and efficacy profile.

#### **4.1 Study Rationale**

This proof-of-principle, placebo-controlled study is designed to evaluate the efficacy, safety, and tolerability of KD025 administered orally for 16 weeks to subjects with moderate to severe chronic plaque psoriasis who are candidates for systemic therapy or phototherapy. Data collected in this study will be used along with data from previous KD025 studies to further evaluate the safety, tolerability, and efficacy of KD025.

Recent studies with KD025 have demonstrated that this molecule has anti-inflammatory activity mediated by the inhibition of secretion of IL-17 and IL-21 by Th17 cells. Since this pathway has emerged as a central inflammatory pathway in psoriasis, it is possible that an oral formulation (e.g., KD025) could offer significant advantages over other available oral formulations. This study will provide safety and efficacy data of the therapeutic response to evaluate the risk/benefit of treating plaque psoriasis with KD025.

#### **4.2 Selection of Doses in this Study**

The only Rho kinase inhibitor that has published human dosing data is fasudil. Fasudil is a moderately selective kinase inhibitor but in contrast to KD025 has activity against both Rho-associated, coiled-coil-containing protein kinase (ROCK1 and ROCK2). The potency of fasudil against ROCK2 is similar to KD025. Fasudil has been marketed in Japan for more than 10 years as an intravenous drug for the prevention of cerebrovascular spasm after stroke. Fasudil was also under development for the treatment of chronic angina. In a Phase 2 clinical study in the US (Vicari et al, 2005), fasudil was dosed from 20 mg three times a day (TID) up to 80 mg TID over 8 weeks. At all doses tested, the adverse events (AEs) in the treatment arm were

reported as no different from placebo. In a separate study to examine endothelial function in subjects and healthy subjects (Nohria et al, 2006), fasudil was dosed at 40 mg TID for 30 days.

The single-ascending dose (SAD)/multiple-ascending dose (MAD) (KD025-101) and MAD (KD025-102) studies support daily dosing with KD025 and have shown a safety profile that allows daily dosing up to 1000 mg per day. In addition, in Study KD025-103, a Phase 1, placebo-controlled study examining the safety, tolerability, and pharmacokinetics (PK) of 500 mg of KD025 administered BID for 28 days in healthy male and post-menopausal female subjects for up to 28 days, the regimen was generally well tolerated.

Pharmacodynamic (PD) studies in these normal healthy subjects have shown biological activity in inhibition of secretion of IL-17 and IL-21 by TH-17 cells in ex vivo stimulated peripheral blood mononuclear cells at the 120-, 240-, and 320-mg dose levels. Thus, the dosing selected in the proposed study (200 mg once daily [QD], 200 mg BID, 400 mg QD, and 600 mg/day) should be both safe and at a level at which biological activity has been measured.

#### **4.3 Previous Clinical Experience with KD025**

A Phase 1 fed or fasted study (KD025-105) was conducted to evaluate the food effect as well as to further evaluate the safety and PK of a single 500-mg dose of KD025 administered orally to fed and fasted healthy males.

Study results showed approximately a 3-fold higher exposure (maximum serum concentration [ $C_{max}$ ] and area under the curve [AUC]) in the fed state compared with the fasted state. There were no treatment emergent adverse events (TEAEs) and no treatment-related AEs were reported in any subject after receiving KD025 in either the fed or fasted state. There were no clinically relevant changes in vital signs, physical examination (PE) findings, or electrocardiogram (ECG) parameters. There were no clinically relevant changes and no clinically meaningful trends in hematology, chemistry, and urinalysis laboratory results attributable to study drug during this study. Plasma concentrations achieved in this study were comparable to plasma levels achieved in previous studies at similar dose levels, where breakfast was provided immediately after dose administration. These studies support dosing KD025 with food.

KD025-205 was a Phase 2a, open-label study in 8 adult subjects with moderately severe psoriasis vulgaris who have failed first-line therapy. As with the other studies, 200 mg QD KD025 administered daily for 28 days was generally safe and well tolerated.

KD025-206 was a Phase 2a, open-label, dose-finding study in 36 adult subjects with moderately severe psoriasis vulgaris who have failed first-line therapy. The study was a 3-month, open-label study with 3 cohorts (200 mg BID, 400 mg QD, and 400 mg BID). KD025 was well tolerated in all subjects and demonstrated activity as measured by PASI. The only adverse experience was related to elevated alanine aminotransferase (ALT)/ aspartate aminotransferase (AST) levels in approximately 20% of the subjects. The KD025 400-mg BID group showed the highest (Grade 3) elevations. The 400-mg BID dose will not be pursued in future studies.

The Investigator's Brochure (IB) 2015 includes additional nonclinical and clinical information about this agent.

#### **4.4 KD025 Nonclinical Toxicology**

KD025 nonclinical toxicology has been characterized in multiple species using a variety of dosing regimens. Details are found in the IB 2015.

#### **4.5 Compliance Statement**

This study will be conducted in compliance with Good Clinical Practice (GCP), including International Conference on Harmonisation (ICH) Guidelines, and in general, consistent with the most recent version of the Declaration of Helsinki. In addition, the investigator agrees to adhere

to all applicable local laws and regulatory requirements relevant to the use of new therapeutic agents in the countries involved.

The study is to be conducted in compliance with the protocol. The appropriate Institutional Review Boards/Independent Ethics Committees (IRBs/IECs) must approve the protocol and any amendments and the subject informed consent form (ICF) prior to implementation.

Freely given written ICF must be obtained from every subject prior to participation in this clinical study. The rights, safety, and well-being of participating subjects are the most important considerations and should prevail over interests of science and society.

Study personnel involved in conducting this study will be qualified by education, training, and experience to perform their respective task(s). This study will not use the services of study personnel where sanctions have been invoked or where there has been scientific misconduct of fraud (e.g., loss of medical licensure, debarment).

## **5 STUDY OBJECTIVES**

### **5.1 Primary Objectives**

The primary objective of the study is as follows:

- To assess the number of subjects that reach PASI 75 after 16 weeks of dosing with various regimens of KD025 compared with placebo

### **5.2 Secondary Objectives**

The following are the secondary objectives of the study:

- To assess changes in absolute PASI scores from baseline to Week 16
- To assess the mean percent change in PASI scores from baseline to Week 16
- To assess safety and tolerability of KD025
- To assess changes in PGA
- To assess changes in DLQI
- To assess changes in PASI scores from baseline to Week 48 for subjects receiving 48 weeks of KD025 treatment
- To evaluate the difference in PASI scores between Week 16 and Week 48 for subjects receiving KD025 for a total of 48 weeks

### **5.3 Exploratory Objective**

The exploratory objective for the study is as follows:

- To evaluate the concentration and changes in IL-17 expression in blood, tissue, and other biomarkers in punch biopsy before and after 16 weeks of dosing with KD025

### **5.4 Study Sites**

This study will be conducted at approximately 20 sites in the US.

### **5.5 Study Endpoints**

The primary safety endpoint will be the percentage of subjects in each treatment group experiencing AEs.

The primary efficacy endpoint for analyses will be the number (%) of subjects with a 75% decrease in PASI by Week 16.

The secondary efficacy endpoints for analysis will include the following:

- A 50% reduction in Week 16 PASI score (PASI 50)
- The mean Week 16 percent change from baseline in PASI
- Improvements in PGA of “clear” or “almost clear” at Week 16
- Improvements in DLQI at Week 16

The exploratory efficacy endpoint is:

- To evaluate the concentration and changes in IL-17 expression in blood, tissue, and other biomarkers in punch biopsy after 16 weeks of dosing with KD025

### 5.6 Overview of Study Design

This will be a Phase 2, double-blind, randomized, placebo-controlled, dose-finding, safety, tolerability, and efficacy study.

This study will be performed in adult male and female subjects with moderate to severe chronic plaque psoriasis who are candidates for systemic therapy or phototherapy. Subjects who have signed an IRB/IEC-approved ICF and met all of the inclusion/exclusion criteria will be enrolled. Approximately 110 subjects will be randomly assigned to each of the 5 dose cohorts in a 1:1:1:1:1 manner to achieve 22 evaluable patients at 16 weeks in each cohort (Table 5-1).

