## 6 STUDY POPULATION

### 6.1 Target Population

Approximately 110 adult male and female subjects (approximately 22 subjects per cohort) will participate in the study. Subjects will be eligible for enrollment as defined by the following inclusion and exclusion criteria.

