### 8.4 Replacements

Subjects withdrawn from the study prior to receiving any study drug will be replaced by enrolling additional subjects into the study.

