2.2 Study Design

This is a Phase 2, double blind, randomized, placebo-controlled, dose-finding, safety, tolerability, and efficacy study.

This study will be performed in adult male and female subjects with moderate to severe chronic plaque psoriasis who are candidates for systemic therapy or phototherapy. Subjects who have signed an Institutional Review Boards/Independent Ethics Committees (IRBs/IECs) approved informed consent form (ICF) and have met all of the inclusion/exclusion criteria will be enrolled. Approximately 110 subjects will be randomly assigned to each of the 5 dose cohorts in a 1:1:1:1:1 manner to achieve 22 evaluable subjects at 16 weeks in each cohort.

Table 1: Cohorts

Cohort	Number of Subjects	Treatment
Cohort 1	~22	200 mg KD025 QD
Cohort 2	~22	200 mg KD025 BID
Cohort 3	~22	400 mg KD025 QD
Cohort 4	~22	600 mg/day KD025 (administered as 400 mg in the morning and 200 mg in the evening)
Cohort 5	~22	Matching placebo BID

Study drug will be orally administered in a double-blind fashion for an initial 16 weeks. All subjects will be given the option to receive KD025 400 mg QD for an additional 32-weeks in an open-label treatment period (week 16 through week 48).

For all subjects, including those who discontinue from the study prematurely, a Follow-Up visit will occur 30 days (\pm 3 days) after the last dose of study drug.

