3.12 Sample Size Justification

A sample size of 36 subjects per cohort receiving KD025 will provide approximately 90% probability of 1 or more subjects in the cohort experiencing an AE that has an underlying rate of $\geq 6\%$ and approximately an 80% probability of 1 or more subjects in the cohort experiencing an AE that has an underlying rate of $\geq 4\%$.

An evaluable sample size of 30 subjects per cohort will provide approximately 85% power to detect a difference in the number of subjects that reach PASI 75 rates at Week 16 between a KD025 group and placebo, assuming rates of 33% and 5%, respectively, at a 5% 2-sided significance level using Fisher's Exact test. This assumes an observed case analysis with approximately 17% of subjects not having a Week 16 PASI score.

But due to newly available plaque psoriasis treatment, this study was terminated early with 110 subjects.

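### About 22 subjects are randomised per cohort to yield 22 evaluable at Week 16, which needs zero loss after dosing; the SAP's own 17% figure implies about 18

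*Protocol*

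**What the plan says.** Protocol 5.6 opens the allocation sentence with "Approximately 110 subjects will be randomly assigned to each of the 5 dose cohorts" and ends it with "in a 1:1:1:1:1 manner to achieve 22 evaluable patients at 16 weeks in each cohort". The synopsis (Methodology) and SAP 2.2 carry the same target: "to achieve 22 evaluable subjects at 16 weeks in each cohort".

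The number randomised per cohort is also 22. Protocol 6.1 states "Approximately 110 adult male and female subjects (approximately 22 subjects per cohort) will participate in the study", and Tables 5-1 and 9-1 list 22 subjects in each of the five cohorts.

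Three other provisions bear on the target:

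- **Replacement.** Protocol 8.4: "Subjects withdrawn from the study prior to receiving any study drug will be replaced by enrolling additional subjects into the study". No rule replaces a subject lost after the first dose.
- **Definition of evaluable.** Protocol 12.3 requires PASI scores at both baseline and Week 16, and no major protocol violation.
- **Expected loss.** SAP 3.12, on its power calculation: "This assumes an observed case analysis with approximately 17% of subjects not having a Week 16 PASI score". That section pairs 36 subjects per cohort with 30 evaluable.

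SAP 3.12 also gives safety detection probabilities for the larger size ("A sample size of 36 subjects per cohort receiving KD025 will provide approximately 90% probability of 1 or more subjects"). It then notes that the study stopped early with 110 subjects and recalculates nothing.

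**The concern.** One number serves as both the randomised and the evaluable size. The two can agree only if every dosed subject reaches Week 16 with a PASI score and no major violation. The plan provides for early discontinuation, does not replace dosed subjects, and has its own attrition figure. At the larger size the SAP kept the two numbers apart (36 and 30); at 110 subjects the distinction is gone.

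At stake is what a reader takes to be the amount of Week 16 information per dose. Someone planning from these documents would expect 22 observed values per arm behind the Week 16 summaries of PASI change, percent change and DLQI. The only attrition figure in the documents points to fewer.

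**Working it through.** **Inputs**

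- Total randomised: about 110 (protocol 5.6, 6.1). Read literally, the 5.6 sentence assigns 110 to each cohort; 6.1 and the cohort tables show that 110 is the total.
- Allocation 1:1:1:1:1 over five cohorts (protocol 5.6).
- Share without a Week 16 PASI: about 17% (SAP 3.12).
- Sizes in the larger plan: 36 per cohort, 30 evaluable (SAP 3.12).

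**Step 1. Reproduce the SAP's own conversion.** Evaluable = enrolled × (1 − loss).
36 × 0.83 = 29.9, which matches the stated 30. In reverse, 6/36 = 16.7%, which matches the stated 17%. The SAP therefore applied the loss between enrolled and evaluable.

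**Step 2. Apply the same conversion to the current size.**
110/5 = 22 randomised per cohort.
22 × 0.83 = 18.3 with a Week 16 PASI (22 × 30/36 = 18.3 as well).
Over the whole trial, 110 × 0.83 = 91.3.
The gap from the stated 22 is 22 − 18.3 = 3.7 per cohort.

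**Step 3. Spread.** If each subject independently has an 83% chance of a Week 16 PASI, the count in a cohort is binomial(22, 0.83), with 2.5th and 97.5th percentiles of 15 and 21. The stated 22 lies above that range.

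**Step 4. Sensitivity to the loss rate.**

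| Loss | Expected per cohort |
|---|---|
| 5% | 22 × 0.95 = 20.9 |
| 10% | 22 × 0.90 = 19.8 |
| 17% | 22 × 0.83 = 18.3 |
| 25% | 22 × 0.75 = 16.5 |

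Only zero loss gives 22. These counts concern the Week 16 PASI alone; removing major violators, as protocol 12.3 requires, can only lower them.

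**Step 5. Effect on the observed-value summaries.** For a given standard deviation, the standard error of a mean scales as 1/√n. √(22/18.3) = 1.10, so standard errors would be about 10% larger than with 22 observed values.

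**Step 6. Adverse-event detection (secondary).** P(at least one case) = 1 − (1 − rate)^n.

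| Rate | SAP, n = 36 | Recomputed, n = 36 | n = 22 |
|---|---|---|---|
| 6% | about 90% | 1 − 0.94^36 = 89% | 1 − 0.94^22 = 74% |
| 4% | about 80% | 1 − 0.96^36 = 77% | 1 − 0.96^22 = 59% |

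At 22 per cohort, the chance of seeing no case of a 6% event rises from 11% to 26%.

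**The case against.** The strongest reply is that the sentence no longer drives anything. Protocol 12.2 and SAP 3.12 present 110 as the result of early termination, so the 22-evaluable phrase determines no enrolment decision. Nor does any SAP analysis use an evaluable population: SAP 3.2 defines only mITT and safety, and the efficacy tables in SAP section 4 are all mITT. This is largely right. It limits the consequence, but the current text still states a size that its own provisions contradict.

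A reader might infer that the primary comparison shrinks to about 18 per arm. The SAP does not support that. SAP 3.8.1 counts a subject without a Week 16 assessment as not reaching PASI 75, and SAP 3.8.2 treats PGA the same way, so about 22 per arm stay in both denominators.

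A reader might also take 18 as a forecast. It is an expectation under an assumption written for the 36-per-cohort plan and for an observed-case analysis. What stands without that figure is that any loss after dosing leaves fewer than 22. The documents' repeated use of approximate counts softens a literal guarantee, but does not turn 18 into 22.

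For the continuous summaries, SAP 3.8.2 reports n and a 95% confidence interval, so the actual count will be visible. LOCF could also restore much of it, because PASI and DLQI are collected at Weeks 4, 8 and 12 and at Early Termination. However, SAP 3.1.2 applies LOCF only where applicable, while SAP 3.1.5 and protocol 12.1 say missing data are generally not imputed. Whether the gap is filled is therefore not settled.

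Finally, it is tempting to call the detection probabilities in SAP 3.12 wrong, or to say that the enrolled number was renamed evaluable when the trial was cut. The probabilities are openly labelled for 36 per cohort and followed by the termination note, so they are out of date rather than false. How the 22-evaluable wording arose cannot be known from these documents.

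**Conclusion.** The inconsistency is real and modest. Three places state that about 22 randomised subjects per cohort will yield 22 evaluable at Week 16. That requires zero loss after dosing, which the replacement rule and the SAP's attrition assumption contradict. Under the 17% figure the expected number with a Week 16 PASI is 18.3 per cohort (95% range 15 to 21, assuming independent losses at the same rate in every arm), and fewer once major violators are removed.

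The consequence is confined to the stated evaluable target and the observed-value Week 16 summaries, and to the latter only if LOCF is not used. The SAP's PASI 75 and PGA denominators are unaffected, and nothing here calls for more subjects. The 36-per-cohort detection probabilities are a secondary matter of keeping SAP 3.12 current.

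**What to change.** In the synopsis (Methodology), protocol 5.6 and SAP 2.2, replace the 22-evaluable phrase with wording such as: *about 22 subjects randomised per cohort; about 18 expected to have a Week 16 PASI if the SAP's 17% assumption holds*. While editing, make clear that 110 is the total across the five cohorts. No enrolment is added; for scale only, expecting 22 with the score at 17% loss would have taken 22/0.83 = 26.5, that is 27 per cohort or 135 in total.

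As a secondary change in SAP 3.12, mark the 36-per-cohort detection probabilities as belonging to the original plan, and add the values for 22 per cohort: about 74% for a 6% event and 59% for a 4% event.

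The cost is wording in two documents. No analysis, population or study procedure changes; the stated figures become less favourable.
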